### 6.2 Intervention Description

Systems Support Mapping (MAP) Intervention. The intervention will be implemented individually to outpatients. Trained facilitators will guide participants to create a visual diagram of their SM activities within their broader life context (MAP). MAP helps participants tangibly see complex SM activities on paper, which makes them more actionable. MAP was acceptable to participants in our preliminary work, which included social and economically marginalized women. Each participant will be provided with a piece of poster-sized paper with five concentric circles on it and six pads of differently-colored sticky notes used to represent different rings. Participants will begin by identifying the most important aspects

## Use of Systems Support Mapping to Guide Patient-Driven Self-Management in Rural and Urban Cancer Survivors

Wake Forest Baptist Comprehensive Cancer Center (WFBCCC)  
WFBCCC # 99118

of life that having cancer is preventing them from experiencing. Each resulting MAP will describe participants' most bothersome life impacts of cancer, SM activities with a focus on non-pharmacologic approaches, facilitators and needs for SM, and outcomes and tradeoffs of SM. We will ask participants to reflect aloud, discuss any discrepancies between current and desired outcomes of SM, and brainstorm about what they need to reconcile them. We will then have participants identify one goal that is important and achievable in the next two weeks and set action steps. [name] (Co-Investigator) will train study staff who have experience with conducting qualitative research (Q-PRO staff) to facilitate MAPs. MAP will take 60-90 minutes, be digitally recorded, and transcribed to ensure treatment fidelity and facilitate analysis. Participants will be *off-treatment* upon completion of this one session.

Reported adverse events and potential risks are described in Section 7.

### 6.3 General Concomitant Medication and Supportive Care Guidelines

This behavioral intervention will not affect usual care.

### 6.4 Duration of Follow Up

Patients will be followed for two weeks after this minimal-risk behavioral intervention is administered for adverse events monitoring. Follow-up for serious adverse events and mortality after the intervention is implemented will take place during the routine clinic visits that the patient will have during the 2 follow-up window (also referenced in Appendix D). If no visit occurs during this window, a phone call confirmation should be made to the patient to determine vital status and whether any adverse events and in particular, Grade 4 unexpected and Grade 5 adverse events occurred during that window of time and recorded on Appendix E.

### 6.5 Criteria for Removal from Study

There are no additional criteria for removal from the study.

## 7.0 Adverse Events List and Reporting Requirements

Expected adverse experiences for the study intervention are as follows:

- Emotional distress (i.e., mild anxiety or mild depressive symptoms)

Each interventionist will monitor and note any adverse events experienced during the MAP session (e.g., patients' expression of emotional distress, request to discontinue the session). The study team will only document adverse events during the two-week period following the intervention.

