### 5.2.7 Clinical factors (cancer type, disease stage, recurrence status, type of treatment) factors will be abstracted from medical charts or self-reported.

## 6.0 Study-Related Activities

### 6.1 Overview of Study-Related Activities

	Pre-Study a	Baseline	MAP b Intervention c	Follow-up (2-week) d
Recruitment	X			
Informed consent	X			
Demographic and Clinical Factors		X		
Patient-Reported Outcomes		X		X
Intervention Completion			X	
Acceptability Ratings				X
Semi-structured Interview				X
Adverse event evaluation			X	X

a Pre-study requirements listed in table must be completed within 30 days prior to registration.

b MAP = Systems Support Mapping

c Intervention may be coordinated with future clinic visit; must be completed within 6 months of registration

d Follow-up visit to be completed 14 - 28 days after intervention

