**What is considered an SAE under this mandatory procedure?**

Any unexpected grade 4 event and all grade 5 events (death during protocol intervention) should be reported. These events should be reported if they occur while a patient is on study treatment or if they occur within 30 days of last study treatment (even if patient begins a new treatment during the 30 days). This window of 30 days should be the standard window to be used in all protocols unless a specific scientific rationale is presented to suggest that a shorter window can be used to identify events. In addition, if it is not clear whether the Grade 4 is unexpected it should be reported.

**Use of Systems Support Mapping to Guide Patient-Driven Self-Management in  
Rural and Urban Cancer Survivors**

Wake Forest Baptist Comprehensive Cancer Center (WFBCCC)  
WFBCCC # 99118

**Table 1: Summary of STRC Reporting Requirements for Institutional Pilot, Phase 1, Phase 2  
and Phase 3 Interventional Trials**

STRC reporting may not be appropriate for specific expected adverse events for protocols. In those situations the adverse events that will not require STRC reporting must be specified in the text of the

	ADVERSE EVENT					
	Grade 1, Grade 2, Grade 3		Grade 4		Grade 5	
	Unexpected	Expected	Unexpected	Expected	Unexpected	Expected
Unrelated	Not Required	Not Required	REPORT TO STRC	Not Required	REPORT TO STRC	REPORT TO STRC
Unlikely	Not Required	Not Required	REPORT TO STRC	Not Required	REPORT TO STRC	REPORT TO STRC
Possible	Not Required	Not Required	REPORT TO STRC	Not Required	REPORT TO STRC	REPORT TO STRC
Probable	Not Required	Not Required	REPORT TO STRC	Not Required	REPORT TO STRC	REPORT TO STRC
Definite	Not Required	Not Required	REPORT TO STRC	Not Required	REPORT TO STRC	REPORT TO STRC

approved protocol.

STRC notification responsibilities of the person (e.g., nurse) handling the reporting/documenting of the SAE in WISER:

1. Make a phone call (or speak in person) to the appropriate clinical member of the STRC as listed below (page if necessary)—see note 2 below

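### Sections 6.4 and 7.0 end adverse event follow-up two weeks after the session, while Appendix D makes unexpected grade 4 and all grade 5 events reportable to 30 days, and no rationale for the shorter window is given.

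*Combined protocol and SAP*

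**What the plan says.** All of the text is in the combined protocol and SAP.

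- **Section 7.0**, on documentation: "The study team will only document adverse events during the two-week period following the intervention". The sentence before it has the interventionist note events that arise during the mapping session.
- **Section 6.4**, on follow-up: "Patients will be followed for two weeks after this minimal-risk behavioral intervention is administered for adverse events monitoring". Serious events and deaths are to be picked up "during the routine clinic visits that the patient will have during the 2 follow-up window (also referenced in Appendix D"). If no clinic visit falls in that window, a telephone call establishes vital status and asks about adverse events, grade 4 unexpected and grade 5 in particular, over the same window.
- **Section 6.1**, schedule: an adverse event evaluation is marked at the session and at the follow-up visit, with the footnote "Follow-up visit to be completed 14 - 28 days after intervention".
- **Section 6.2**: a participant is off treatment once the single session is complete.
- **Section 7.2** refers to Appendix D for the events that the Safety and Toxicity Reporting Committee (STRC) reviews.
- **Appendix D**, definition of a reportable SAE: unexpected grade 4 and all grade 5 events are to be reported if they occur on study treatment or "if they occur within 30 days of last study treatment (even if patient begins a new treatment during the 30 days"). It makes 30 days the standard for all protocols "unless a specific scientific rationale is presented to suggest that a shorter window can be used to identify events".

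**The concern.** Two parts of one protocol set different end dates for looking after the same session. The operational sections, which staff work from, stop at two weeks. The reporting rule, which the protocol adopts, runs to 30 days for its most serious events. Section 6.4 makes this harder to notice because it cites Appendix D as though the two windows agreed.

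What is at stake is active ascertainment of a narrow class of events. A site that follows Sections 6.4 and 7.0 exactly has no instruction to ask about an unexpected grade 4 event or a death between day 15 and day 30. Such an event would reach the STRC only if someone on the team happened to learn of it. Table 1 of Appendix D requires these reports at every attribution level, including unrelated, so the low risk of the intervention does not take them out of scope.

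**Working it through.** The plan gives no figure of its own to reproduce. The check compares the stated windows, in days from the end of the session.

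**Inputs**

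| Item | Value | Source |
|---|---|---|
| End of study treatment | day 0 (end of the one session) | Section 6.2 |
| Adverse event follow-up and documentation | to day 14 | Sections 6.4 and 7.0 |
| Follow-up visit, with adverse event evaluation | day 14 to day 28 | Section 6.1 |
| STRC reporting window, unexpected grade 4 and all grade 5 | to day 30 | Appendix D |
| Planned enrolment | 24 | Sections 2.0 and 9.3 |

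**Step 1. Is Appendix D's exception invoked?** A shorter window needs a specific scientific rationale. The nearest wording is the phrase minimal-risk in Section 6.4. It describes the intervention; it is not offered as a reason for two weeks, and neither Section 6.4 nor Section 7.0 acknowledges a departure from 30 days. On the text as it stands, the default applies.

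**Step 2. Gap if Sections 6.4 and 7.0 are followed literally.** Gap = end of reporting window − end of documentation = 30 − 14 = 16 days (days 15 to 30), and 16 / 30 = 53% of the post-session reporting window. The telephone call does not shorten this, because it asks about the same two-week window.

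**Step 3. Gap if the follow-up visit records everything up to its own date.** With the visit on day *v*, gap = 30 − *v*.

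- *v* = 14: 30 − 14 = 16 days.
- *v* = 28: 30 − 28 = 2 days.

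The gap is therefore 2 to 16 days, depending on the visit date. No permitted visit date closes it fully.

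**Step 4. Scale.** If all 24 participants complete the session, the reporting window holds 24 × 30 = 720 person-days. The part without active ascertainment is between 24 × 2 = 48 and 24 × 16 = 384 person-days. These are shares of time, not of events. The documents give no event rate, so no expected count can be derived.

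**The case against.** The strongest reply is that two different duties are being compared. Section 7.0 governs study documentation of adverse events in general; Appendix D sets a committee-reporting trigger for a small subset. Appendix D also says that its own rules alone decide what goes to the STRC, that all adverse events on the trial are entered in WISER, and that whoever observes a qualifying event must see that it is reported. Section 7.3 requires IRB reporting of unanticipated problems and gives no two-week limit. This part stands. A reader might infer that a known day-20 death would go undocumented or be discarded; the documents do not support that. What they leave open is whether anyone asks.

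Several other inferences are tempting and also fail.

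- *The day 14-28 visit contradicts the two-week window.* It need not. A visit that looks back over two weeks has to fall on or after day 14. The text is silent on what happens to later events disclosed there, and no passage tells staff to drop them.
- *Events during the session are excluded by the word only in Section 7.0.* The preceding sentence and the Section 6.1 schedule both cover them.
- *The missing unit in Section 6.4 creates a further window.* The phrase "during the 2 follow-up window" has lost a word, and the sentence before it supplies two weeks. This is clerical.
- *The 53% measures missed events.* It is a share of calendar days under the literal reading, and it falls as the visit moves later.
- *A planned result is affected.* Section 5 lists no adverse event outcome and Section 9 plans no adverse event analysis.

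It can also be argued that minimal risk, with only mild emotional distress listed as expected, is rationale enough. Whether it would satisfy the institution is for its committee to judge. The protocol has not put the argument, and Appendix D asks for it to be presented.

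**Conclusion.** The inconsistency is real and sits in current text. Sections 6.4 and 7.0 stop at two weeks. Appendix D runs to 30 days for unexpected grade 4 and all grade 5 events unless a rationale is presented, and none is. Section 6.4 cites Appendix D for a window that Appendix D does not contain.

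The consequence is limited to active ascertainment of those events: up to 16 days unasked, or 2 to 16 if the visit records events to date. This rests on two readings. The 30-day clock starts at the end of the single session, and the words minimal-risk do not by themselves amount to the rationale that Appendix D requires. Few such events are likely with 24 participants and one behavioural session; that is a judgement, since the documents give no rate. The point is worth correcting because following one section to the letter leaves part of a mandatory reporting window unwatched. It is not evidence that observed events would be lost, and it does not say which window is right.

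**What to change.** Reconcile Sections 6.1, 6.4, 7.0 and Appendix D to one stated ascertainment window for unexpected grade 4 and grade 5 events. Appendix D itself offers two routes, and the choice between them belongs to the sponsor and the committee:

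1. match the window in Sections 6.4 and 7.0 to Appendix D for these events; or
2. keep a shorter window and write in the specific scientific rationale that Appendix D requires, correcting the cross-reference in Section 6.4 so that it no longer implies the windows agree.

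Under either route, state that events disclosed at the day 14-28 visit are recorded, and up to what date. The missing unit in Section 6.4 can be restored in the same edit.

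The cost is protocol wording. The first route may also need one later check per participant, for which Section 6.4 already provides a telephone route.

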### 7.1 Adverse Event Characteristics

- CTCAE term (AE description) and grade: The descriptions and grading scales found in the revised NCI Common Terminology Criteria for Adverse Events (CTCAE) version 4.0 will be utilized for AE reporting. All appropriate treatment areas should have access to a copy of the CTCAE version 4.0. A copy of the CTCAE version 4.0 can be downloaded from the CTEP web site (<http://ctep.cancer.gov>).

## **Use of Systems Support Mapping to Guide Patient-Driven Self-Management in Rural and Urban Cancer Survivors**

Wake Forest Baptist Comprehensive Cancer Center (WFBCCC)  
WFBCCC # 99118

- ‘Expectedness’: AEs can be ‘Unexpected’ or ‘Expected’ (see Section 7.1 above) for expedited reporting purposes only.
- Attribution of the AE:
  - Definite – The AE is clearly related to the study treatment.
  - Probable – The AE is likely related to the study treatment.
  - Possible – The AE may be related to the study treatment.
  - Unlikely – The AE is doubtfully related to the study treatment.
  - Unrelated – The AE is clearly NOT related to the study treatment.

### **7.2 STRC SAE Reporting Requirements**

The Safety and Toxicity Reporting Committee (STRC) is responsible for reviewing SAEs for WFBCCC Institutional studies as outlined in Appendix D. STRC currently requires that all unexpected 4 and all grade 5 SAEs on these trials be reported to them for review. All WFBCCC Clinical Research Management (CRM) staff members assisting a Principal Investigator in investigating, documenting and reporting an SAE qualifying for STRC reporting are responsible for informing a clinical member of the STRC as well as the entire committee via the email notification procedure of the occurrence of an SAE.

### **7.3 WFUHS IRB AE Reporting Requirements**

Any unanticipated problems involving risks to subjects or others and adverse events shall be promptly reported to the IRB, according to institutional policy. Reporting to the IRB is required regardless of the funding source, study sponsor, or whether the event involves an investigational or marketed drug, biologic or device. Reportable events are not limited to physical injury, but include psychological, economic and social harm. Reportable events may arise as a result of drugs, biological agents, devices, procedures or other interventions, or as a result of questionnaires, surveys, observations or other interactions with research subjects.

All members of the research team are responsible for the appropriate reporting to the IRB and other applicable parties of unanticipated problems involving risk to subjects or others. The Principal Investigator, however, is ultimately responsible for ensuring the prompt reporting of unanticipated problems involving risk to subjects or others to the IRB. The Principal Investigator is also responsible for ensuring that all reported unanticipated risks to subjects and others which they receive are reviewed to determine whether the report represents a change in the risks and/or benefits to study participants, and whether any changes in the informed consent, protocol or other study-related documents are required.

Any unanticipated problems involving risks to subjects or others occurring at a site where the study has been approved by the WFUHS IRB (internal events) must be reported to the WFUHS IRB within 7 calendar days of the investigator or other members of the study team becoming aware of the event.

Any unanticipated problems involving risks to subjects or others occurring at another site conducting the same study that has been approved by the WFUHS IRB (external events) must be reported to the WFUHS IRB within 7 calendar days of the investigator or other members of the study team becoming aware of the event.

Any event, incident, experience, or outcome that alters the risk versus potential benefit of the research and as a result warrants a substantive change in the research protocol or informed consent process/document in order to insure the safety, rights or welfare of research subjects.

**Use of Systems Support Mapping to Guide Patient-Driven Self-Management in  
Rural and Urban Cancer Survivors**

Wake Forest Baptist Comprehensive Cancer Center (WFBCCC)  
WFBCCC # 99118

## 7.4 Sponsor Reporting Requirements

There are no additional sponsor reporting requirements.

## 8.0 Data Management

Informed consent document	EPIC
Decline Forms	REDCap
Screening Log	File on a Secure Server
Protocol Registration Form	WISER/OnCore
Demographic and Clinical Factors	REDCap
Patient-reported Outcomes	REDCap
Intervention Completion Form	REDCap
Intervention MAP	Files on a Secure Server
Semi-structured Interview	Files on a Secure Server
Adverse Events Log	WISER/OnCore

## 9.0 Statistical Considerations

### 9.1 Analysis of Primary Objective

**9.1.1** We will use one-sample tests of negative binomial probabilities and binomial proportions to compare rates of feasibility to hypothesized values. Rates will be summarized using point estimates and 95% confidence intervals. In exploratory analyses, we will compare participants' intervention completion and retention by baseline characteristics using chi-square tests and t-tests.

### 9.2 Analysis of Secondary Objectives

To meet Objective 2.2.1, we will use descriptive statistics to summarize participant ratings of acceptability.

Descriptive statistics (means, standard deviations, 95% confidence intervals) will be used to summarize proximal outcomes and change in health outcomes by assessment measure to meet Objective 2.2.2. The primary interest will be in estimating the variance for use in planning future studies.

For Objective 2.2.3, the internal study team will work with external collaborators through an iterative process to facilitate a qualitative content analysis of the large quantity of textual MAP data. Specifically, we will first enter text data from the completed paper maps into a software program co-developed by [name] (external Senior Programmer, University of North Carolina-Chapel Hill Renaissance Computing Institute) and [name] (Consultant) using the *ssm* function to create a digital map. [name] will translate the text MAP data into lists that can be sorted by the study team (using the *sort* program). The *sort* program will allow us to group and code similar terms or concepts. Next, we will send our *sort* files back to [name] and he will use Python programming language to help aggregate the large amounts of textual

## Use of Systems Support Mapping to Guide Patient-Driven Self-Management in Rural and Urban Cancer Survivors

Wake Forest Baptist Comprehensive Cancer Center (WFBCCC)  
WFBCCC # 99118

data into formats we can manipulate (Python Software Foundation, 2017). These matrices will be saved in the form of Excel (.csv) files, which are compatible with other statistical software. We will ultimately present resulting counts and descriptive statistics of findings alongside descriptive categories and themes.

To meet Objective 2.2.4, we will also conduct a qualitative content analysis. Qualitative data will be sent to an external vendor to be transcribed. Two internal study team members will double-code at least 10% of coding of transcripts from the semi-structured interviews and resolve any disagreements to ensure that we achieve robust and unbiased results. We will evaluate qualitative and quantitative analyses in a mixed-methods framework for consistency and discrepancies across all analyses to refine the protocol.

To meet Objective 2.2.5, we will examine all quantitative and qualitative analyses by urban-rural status as classified using the Federal Office of Rural Health Policy definition of rural. For quantitative measures, we will compute descriptive statistics by urban-rural status and will use Fisher's exact tests and Wilcoxon rank sum tests to compare urban and rural participants. Qualitative results will be summarized by urban-rural status. We will also compare MAP results by rural-urban status.

### 9.3 Power and Sample Size

The target sample size is based on estimating rates of feasibility measures to inform the design of an efficacy trial. If the recruitment rate is below 50% and intervention completion and retention rates are below 70%, a larger study may not be feasible. Assuming a negative binomial distribution and true rate of 50%, the probability that we would have to approach 61 or more people to recruit 24 is <0.05. Therefore, if we approach  $\geq 61$  participants to enroll 24, it is unlikely the true probability is above 50%, and we will conclude the study may not be feasible. Out of the 24 participants, if the true rate of intervention completion and study retention is 70%, we expect 13 or more will participate/be retained, so if 12 or fewer do not participate/are not retained the study may not be feasible; we have 80% power to test that the hypothesis that the rate is 70% compared to the alternative that is 46% or less. The number of participants interviewed will be determined when theoretical saturation is reached. We estimate that we will need 8-12 participants in each group (rural-urban).

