### 2.1 Primary Objective

2.1.1 To evaluate the feasibility of the MAP intervention in colorectal cancer survivors, as characterized by enrollment, intervention adherence, and retention rates.

*We hypothesize >50% of eligible patients will enroll and that >70% of participants will complete the intervention and be retained in the study.*

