### 5.1 Primary Outcome (Feasibility)

Enrollment rate will be calculated as the percent of eligible participants approached who agree to participate.

Participation rate will be calculated as the percent of participants who complete the study intervention among those enrolled.

Retention rate will be calculated as the number of participants who complete the study measures among those enrolled.

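### Section 9.3 joins the three feasibility criteria with *and*, but its numeric rules let a single miss count; the sentence should say *or*, and the inverted 12-of-24 rule should be corrected in the same edit

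*Combined protocol and SAP*

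**What the plan says.** Feasibility is the only primary objective. Section 2.1.1 states the hypothesis: "We hypothesize >50% of eligible patients will enroll and that >70% of participants will complete the intervention and be retained in the study". Section 5.1 defines enrollment, participation and retention as three rates, the last two each among those enrolled. Section 9.1 tests the rates against their hypothesized values and reports 95% confidence intervals. It gives no rule for combining the results.

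Section 9.3 is the only text that turns the rates into a conclusion, and it does so in three steps:

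- A general sentence: "If the recruitment rate is below 50% and intervention completion and retention rates are below 70%, a larger study may not be feasible".
- A recruitment rule. At a true rate of 50%, "the probability that we would have to approach 61 or more people to recruit 24 is <0.05". If that many are approached, "it is unlikely the true probability is above 50%, and we will conclude the study may not be feasible". Nothing is required of completion or retention.
- A completion and retention rule: "so if 12 or fewer do not participate/are not retained the study may not be feasible". Nothing is required of recruitment. The power statement attached to it is "we have 80% power to test that the hypothesis that the rate is 70% compared to the alternative that is 46% or less".

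**The concern.** The general sentence and the numeric rules fit poorly together. Taken as the criterion, the general sentence asks for recruitment, completion and retention all to fall short. Taken as the criterion, the numeric rules ask for any one of them to do so.

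The gap matters most when uptake is poor but those who enroll stay in. That is a plausible pattern for a single 60-90 minute session with one short follow-up. Suppose 65 people are approached to enroll 24 (24/65 = 36.9%) and 22 of the 24 complete and are retained. The recruitment rule says a larger study may not be feasible. The general sentence, read as the criterion, does not. Because the plan does not settle which governs, the choice could be made after the data are seen, and on the primary question.

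A second wording fault sits in the same place. The completion and retention rule counts people who do *not* participate, which reverses its meaning. A switch to any-miss wording would carry that error into the overall conclusion.

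**Working it through.** **Inputs.** From section 9.3: 24 to be enrolled, recruitment reference rate 0.50, cut-off 61 approached, completion and retention reference rate 0.70, cut-off 12 of 24, alternative 0.46. Assumed for illustration, because the plan gives no such scenario: true uptake of 30%, 35% or 40% with completion and retention of 80%. Recruitment is assumed independent of completion and retention.

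**Step 1: reproduce the plan's figures.** Needing 61 or more approaches means that at most 23 of the first 60 people enroll.

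- P(Bin(60, 0.50) ≤ 23) = 0.0462. For a cut-off of 60 the probability is 0.0587, so 61 is the smallest cut-off below 0.05. The observed rate at the cut-off is 24/61 = 39.3%.
- P(Bin(24, 0.70) ≤ 12) = 0.0314, so 13 or more is expected with probability 0.969. This shows that the intended rule counts 12 or fewer who *do* participate or are retained.
- The 80% power reproduces by the normal approximation at one-sided 5% (80.1%). The exact power of the 12-or-fewer rule at 46% is 72.6%.

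**Step 2: how completion and retention are related.** Section 5.0 collects the follow-up measures two weeks after the mapping session, and section 6.1 times that visit at 14 to 28 days after the intervention. The follow-up questionnaire in Appendix F rates the mapping exercise and its facilitator. Someone who never has the session cannot supply these data, so those retained are in effect a subset of those who complete. It follows that:

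- 12 or fewer completing implies 12 or fewer retained;
- *any miss* reduces to recruitment or retention missing;
- *all miss* reduces to recruitment and completion missing.

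**Step 3: poor uptake, good retention.** P(Bin(24, 0.80) ≤ 12) = 0.00098.

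| True uptake | Recruitment rule fires, P(Bin(60, p) ≤ 23) | All three miss (× 0.00098) |
|---|---|---|
| 40% | 0.451 | 0.0004 |
| 35% | 0.753 | 0.0007 |
| 30% | 0.937 | 0.0009 |

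At 35% uptake the two readings would differ in about 75% of studies.

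**Step 4: false-flag probability on target.** Take recruitment at exactly 50% and retention at 70%.

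- Any miss: 1 − (1 − 0.0462)(1 − 0.0314) = 1 − 0.9538 × 0.9686 = 0.076.
- All miss, with completion also at 70%: 0.0462 × 0.0314 = 0.0015. This is an upper bound, since completion cannot be below retention.

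**Step 5: the inverted rule.** Read literally, the rule is met when 12 or fewer of 24 do not participate. At a true rate of 70%, P(Bin(24, 0.30) ≤ 12) = 0.988.

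**The case against.** The strongest reply is that nothing here is contradictory. The general sentence says what follows *if* all three rates fall short. It does not say *only if*, and a statement of that form is compatible with a rule under which one shortfall is enough. That is correct. A reader might infer that section 9.3 makes infeasibility depend on all three failing and then contradicts itself, but the text does not go that far. It also says that a larger study *may not* be feasible, which is softer than calling it infeasible.

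It is also fair to say that the intended reading can be recovered. Every rule with a number works per measure, including the completion and retention rule as well as the recruitment rule. Section 9.1 tests rates against their own values, and the hypothesis in section 2.1.1 fails if any part fails. This stands, and it identifies *and* as the outlier. It does not remove the need to edit, because the primary decision rule should not have to be inferred, and section 9.3 does say that the team will draw a conclusion from it.

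Finally, the on-target error rate is a boundary case. Section 9.4 cites over 75% uptake in the team's current study. At 60% true uptake the recruitment rule fires with probability 0.0006, and at 75% with about 2 × 10⁻⁹. A combined error rate is therefore optional in a pilot that reports estimates with confidence intervals.

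**Conclusion.** The point holds as an ambiguity in the only go/no-go text, with minor to moderate severity. If the general sentence is taken as the criterion, poor uptake with good retention passes unflagged. At assumed true rates of 35% and 80%, the recruitment rule fires with probability 0.75 against under 0.001 for all three missing. The assumptions are independence of recruitment from the later measures and the illustrative true rates.

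Two further inferences are tempting and are not supported.

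- A reader might treat completion and retention as independent. That would raise the any-miss false-flag probability to 10.5% and give a joint rate of 0.70 × 0.70 = 49% for completing and being retained. The follow-up schedule and questionnaire make retention nested in completion, so the figure is about 7.6% and the joint rate is simply the retention rate.
- A reader might see section 2.1.1 as a third, competing criterion because it says ">70% of participants will complete the intervention and be retained in the study". The objective in that same section lists enrollment, adherence and retention as separate rates, in line with section 5.1, so no change is needed there.

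**What to change.** Make two edits in section 9.3, together.

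1. In the general sentence, replace *and* with *or* throughout, so that a larger study may not be feasible if any one of the three criteria is missed: recruitment below 50%, completion below 70%, or retention below 70%.
2. In the completion and retention rule, remove the negatives, so that it is met when 12 or fewer of the 24 participate or are retained. Without this second edit, the any-miss rule read literally would flag nearly every on-target study.

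Optionally, add the combined false-flag probability: about 7.6% with recruitment at exactly 50% and retention at 70%, made up of 0.046 and 0.031, with retention nested in completion and recruitment assumed independent.

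The cost is wording only. Sample size, cut-offs, data collection and section 2.1.1 stay as they are. If the combined probability is printed, it will be somewhat higher than the single-test figure of under 0.05 that the section gives now.
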